5.1. Hypotheses and Decision Rules

In this study, all hypothesis testing will be one-sided with Type I error of 0.025.

The primary objective is to evaluate the efficacy of a single infusion of PF-07055480 in participants ≥ 18 and < 65 years of age with moderately severe to severe hemophilia A (FVIII:C $\leq 1\%$).

For the primary efficacy analysis, the hypothesis testing written in statistical notation is:

H_0 : Total ABR_{PF-07055480} – Total ABR_{FVIII prophylaxis} ≥ 3.0 versus H_a : Total ABR_{PF-07055480} – Total ABR_{FVIII prophylaxis} < 3.0

where Total ABR_{PF-07055480} represents the mean Total ABR post PF-07055480 infusion, while Total ABR_{FVIII prophylaxis} represents the mean Total ABR on prior routine prophylaxis FVIII replacement. The proposed non-inferiority margin is 3.0 bleeds/year.

If the upper bound of the confidence interval of the difference (Total ABR_{PF-07055480} – Total ABR_{FVIII prophylaxis}) is less than 3.0, the noninferiority would be demonstrated.

For the key secondary endpoint (FVIII activity level $> 5\%$), the percentage of participants with FVIII activity level at 15 months post PF-07055480 infusion will be compared to the null hypothesis of percentage $\leq 68\%$ using an exact test for binomial proportion. The other key secondary endpoint (Treated ABR) will be tested for noninferiority using the same method and margin as described above for the Total ABR.

A gatekeeping process will be applied to control for multiple endpoint comparisons at the primary analysis. The subsequent hypothesis testing will only be performed after success on the previous hypothesis test. The testing ceases when a failure occurs. The sequence of gatekeeping process is displayed in Table 8 below. Note that only selected endpoints are included in the sequence.

Table 8. Gatekeeping Sequence

Order in the testing sequence	Statistical testing
1	Non-inferiority in Total ABR from Week 12 [Day 78] through at least 15 months (up to data cutoff) postinfusion compared to prior prophylaxis treatment with a NI margin of 3
2	Percentage of participants with FVIII activity $> 5\%$ at 15 months postinfusion compared to the null hypothesis of percentage $\leq 68\%$
3	NI in Treated ABR from Week 12 [Day 78] through at least 15 months (up to data cutoff) postinfusion compared to prior prophylaxis treatment with a NI margin of 3
4	Superiority in AIR from Week 12 [Day 78] through at least 15 months (up to data cutoff) postinfusion compared to prior prophylaxis treatment
5	Superiority in Annualized FVIII consumption (IU/kg) from Week 12 [Day 78] through at least 15 months (up to data cutoff) postinfusion compared to prior prophylaxis treatment
6	Superiority in Treated ABR from Week 12 [Day 78] through at least 15 months (up to data cutoff) postinfusion compared to prior prophylaxis treatment
7	Superiority in Total ABR from Week 12 [Day 78] through at least 15 months (up to data cutoff) postinfusion compared to prior prophylaxis treatment

8	Haem-A-QoL Physical Health domain score significantly improved from baseline at 12 months postinfusion
9	HAL Complex Lower Extremity Activities domain score significantly improved from baseline at 12 months postinfusion

5.2. General Methods

Most safety evaluations are obtained via comparison of participants' baseline with data collected post PF-07055480 infusion in this study. Baseline is defined as the most recent observation collected prior to PF-07055480 infusion.

Efficacy assessments that compare experiences before and after PF-07055480 infusion will use data collected from the lead-in study C0371004 and preinfusion of PF-07055480 in C3731003 (while participants are on a regular FVIII prophylaxis regimen). FVIII activity is assessed by visit. Analysis details provided in [Section 6](#) are for the primary analysis unless specified.

5.2.1. Analyses for Binary Endpoints

Descriptive statistics of binary data will include the number of non-missing observations, the frequency of the observed endpoint as well as the observed percentage. The two-sided 95% confidence interval (CI) of the observed percentage will be provided (when appropriate) using the exact binomial method.

5.2.2. Analyses for Continuous Endpoints

The n, mean, median, standard deviation, Q1, Q3, minimum (min), maximum (max), and 95% CI of mean (when appropriate) for the observed value and the change from baseline by visit will be provided in the summary tables.

5.2.3. Analyses for Categorical Endpoints

In general, counts and percentages will be presented for categorical variables.

5.3. Methods to Manage Missing Data

In general, missing data will not be imputed in this study, unless specified in [Section 3](#) and [Section 6](#), where individual endpoints are discussed.

6. ANALYSES AND SUMMARIES

This section describes analysis details for the primary analysis.

6.1. Primary Endpoint

6.1.1. Total Annualized Bleeding Rate

6.1.1.1. Main Analysis

Total ABR will be analyzed using a repeated measures generalized linear model with negative binomial distribution, identity link function and generalized estimating equation (GEE) model form to account for within-participant correlation. Number of bleeds within

the given follow-up period will be the dependent variable in the model. ‘Year’ and an interaction of year by treatment (treatment of prophylaxis or PF-07055480) will be included in the model. ‘Year’ is a numeric measure of time in the unit of year in the given follow-up period. ‘Treatment’ will be a class factor in the model, and ‘subject’ (i.e., participant) will be a random effect. No other covariates will be included in the model. Detailed specification for the model and parameters is provided in [Appendix 1.1](#).

- The ‘Efficacy’ population will be the main analysis population for the primary analysis.
- The Total ABR from Week 12 [Day 78] through at least 15 months (up to data cutoff) post PF-07055480 infusion will be compared to participants’ Total ABR on prior FVIII prophylaxis regimen before infusion. The estimation of difference and CI will be constructed. If the upper bound of the confidence interval of the difference of (Total ABR _{PF-07055480} – Total ABR _{FVIII prophylaxis}) is less than 3.0, then statistical significance of the noninferiority would be demonstrated. An example of SAS code of such analysis is included in [Appendix 1.2](#). If noninferiority is demonstrated, further testing for superiority would be conducted, using the same method, except the margin would be set to 0.

The summary table will include two columns, for FVIII prophylaxis (pre-PF-07055480) and PF-07055480 (post-PF-07055480), respectively. The descriptive statistics including n, mean, standard deviation, median, Q1, Q3, min, max of the observed Total ABR, estimated means with 95% CI of estimated means (model derived), estimated difference in mean Total ABRs (model derived), one-sided p-value, and the 95% CI of the difference in mean Total ABRs (model derived) will be presented in the summary table. In addition, percent reduction in mean Total ABR, one-sided p-value, and the corresponding 95% CI will be estimated from a separate analysis model with log link function. An example of SAS code for this analysis model is provided in [Appendix 1.3](#).

6.1.1.2. Sensitivity/Supplementary Analyses

The following sensitivity analyses will be performed for Total ABR in the primary analysis without hypothesis testing unless specified:

- The same analysis model and summary as described above for the main analysis will be repeated on the Total ABR from Week 12 through data cutoff, using the ‘Dosed’ population regardless of the length of follow-up in preinfusion or postinfusion.
- Same analysis as described for the main analysis will be performed on the Total ABR from Week 12 through data cutoff, using the ‘Evaluable’ population if it is different from the ‘Dosed’ population.
- Two sensitivity analyses will be performed to include the bleeding data collected during only the latest 6 months and the first 6 months separately during the lead-in study up to preinfusion of PF-07055480 in order to support the robustness of the primary analysis results and confirm the absence of seasonal effect, using the

‘Efficacy’ population. In these sensitivity analyses, all the participants will have the same length (i.e., 6 months) of preinfusion observation period.

- Include only the data collected in the lead-in study (C0371004) (i.e., excluding the preinfusion data in C3731003) and the data postinfusion of PF-07055480 using the same analysis model as described above. This analysis will be conducted on the ‘Efficacy’ population.

Additional US-specific analyses are described in [Appendix 1.4](#).

Supplementary analyses (to be conducted on the ‘Efficacy’ population): Total ABR 15 months, Year 2, Year 3, Year 4, and Year 5 as defined in [Section 3.1.1](#), as well as Total ABR in cumulative follow-up intervals (i.e., from Week 12 [Day 78] through 2 years postinfusion, from Week 12 [Day 78] through 3 years postinfusion, etc.), will be compared separately to Total ABR of FVIII prophylaxis (pre-PF-07055480) using the same statistical method as for Total ABR as described in [Section 6.1.1.1](#) except that noninferiority test or superiority test won’t be performed. For analyses by yearly interval, participants who have discontinued from the study or resumed prophylaxis regimen prior to the start of a given yearly interval will be excluded.

The descriptive statistics including n, mean, standard deviation, median, Q1, Q3, min, max of the observed Total ABR, estimated means with 95% CI of estimated means (model derived), estimated difference in mean Total ABRs (model derived), and the 95% CI of the difference in mean Total ABRs (model derived) will be presented in the summary table.

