2.3. Study Design

Study C3731003 is a Phase 3, open-label, multicenter, single arm study to evaluate the efficacy and safety of a single infusion of PF-07055480 in adult male participants with moderately severe to severe hemophilia A (FVIII:C \leq 1%).

Eligible study participants will be followed while on routine FVIII prophylaxis therapy in the lead-in Study C0371004 in order to collect pretreatment (established usual care) data for efficacy and selected safety parameters.

This study will include an approximately 6-week screening (screening can be extended beyond 6 weeks when needed) and baseline period followed by the dosing day (Day 1), a 2-year efficacy and safety observation period (short term monitoring), and a 3-year long-term monitoring period.

This study will enroll approximately 70 eligible participants from Study C0371004 to achieve at least 50 dosed participants who complete at least 15 months of follow-up postinfusion in this study (C3731003). These 50 participants will have completed at least 6 months of routine prophylaxis follow up in Study C0371004. The duration of follow up for subsequent participants in the lead-in study (C0371004) may be shorter than 6 months after at least 50 hemophilia A participants are expected to reach 15 months postinfusion in this study (C3731003). The study design is displayed in [Figure 1](#) below.

[figure not shown]
The primary analysis will be conducted when at least 50 dosed participants have reached at least 15 months of follow-up postinfusion, corresponding to at least 12 months of follow-up for these 50 dosed participants after the estimated FVIII activity steady state onset. The onset of FVIII activity steady state based on the C3731001 study data is expected to be reached at the beginning of Week 9 postinfusion. However, as a conservative approach, the beginning of steady state will be considered as Week 12 (i.e., approximately 3 months) for the primary analysis.

A final analysis will be conducted when all dosed participants have completed the entire study (i.e., 5 years in follow-up duration per participant) or discontinued prematurely from the study.

The study may be paused in the event of a confirmed inhibitor level or a thrombotic event suspected to be related to $>$ upper limit of normal (ULN) for FVIII activity levels for a participant as described in the Protocol Sections 8.1.2.3 and 8.2.6.2.

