4. ANALYSIS SETS (POPULATIONS FOR ANALYSIS)

For purposes of analysis, the following populations are defined:

Population	Description	Applicable Analysis (for additional information refer to Section 6)
Enrolled	All participants who sign the informed consent form (ICF) and meet all inclusion/exclusion criteria.	Disposition events summary
Dosed/Safety	All participants enrolled in the study and who receive the study intervention.	Demographic and baseline characteristics, hemophilia history, medical history, safety, nAbs, ADA, FVIII antigen, von Willebrand factor, vector shedding assessments, joint health assessments, efficacy sensitivity/supplementary analyses, PRO analyses, and coagulation activation tests.
Evaluable	
All participants enrolled in the study and who receive the study intervention and have no significant interruption of efficacy measurement.
 
The ‘Evaluable’ analysis population will include participants who receive the study intervention (full dose of infusion) and exclude participants with significant interruption of efficacy measurement. The significant interruption would occur if the participant discontinues from the study, is lost to follow-up, has significant
	Efficacy sensitivity/supplementary analyses

Population	Description	Applicable Analysis (for additional information refer to Section 6)
	interruption in data collection, or has a major protocol deviation.	
Efficacy	All participants in the 'Dosed' population who have completed at least 6 months of follow up in the lead-in study and at least 15 months of follow up or discontinued from the study C3731003 prior to the data cutoff for reporting.	Main analysis population for efficacy
Ultrasound Substudy	All participants who sign the additional ICF for the ultrasound substudy and meet all inclusion/exclusion criteria, and the participant's joint ultrasound have been reviewed following the extended ultrasound scale at baseline, and any data post-baseline.	HEAD-US ultrasound scale - total score and subscores, demographic and baseline characteristics, AEs, disposition, and FVIII activity level data.
Vector Shedding Substudy	All participants who sign the additional ICF for the Vector Shedding substudy and meet all inclusion/exclusion criteria, and who provide any additional vector shedding data for analysis.	Shedding vector levels in PBMC, saliva, urine, semen, and plasma; demographic and baseline characteristics, AEs, disposition, and FVIII activity level data.

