Appendix 2. Summary of Efficacy/PRO Analyses

Endpoint	Analysis Type	Population	Data Inclusion and Rules for Handling Intercurrent Events and Missing Data	Analysis
Total ABR (from Week 12 through at least 15 months [up to data cutoff] postinfusion of PF-07055480)	Primary analysis: main analysis	Efficacy	
 Any data after the resumption of FVIII prophylaxis regimen (if necessary) will be excluded. Data after study discontinuation won't be imputed. 	A generalized linear model with repeated measures with negative binomial distribution and identity link function to demonstrate non-inferiority to prior FVIII prophylaxis regimen with a NI margin of 3.0 bleeds/year. If noninferiority is demonstrated, further testing for superiority would be conducted.
Total ABR (from Week 12 through data cutoff postinfusion of PF-07055480)	Primary analysis: sensitivity analysis	Dosed	Same as for the main analysis.	Same as above but no hypothesis testing.
Total ABR (from Week 12 through data cutoff postinfusion of PF-07055480)	Primary analysis: sensitivity analysis	Evaluable	Same as for the main analysis.	Same as above but no hypothesis testing.
Total ABR postinfusion (from Week 12 through at least 15 months [up to data cutoff] postinfusion of PF-07055480) compared to separately the first and the latest 6 months preinfusion data	Primary analysis: sensitivity analysis	Efficacy	Same as for the main analysis. To include the bleeding data collected during only the latest 6 months and the first 6 months separately during the lead-in study up to preinfusion of PF-07055480 in the 'Efficacy' population.	Same as above but no hypothesis testing.
Total ABR postinfusion (from Week 12 through at least 15 months [up to data cutoff] postinfusion of PF-07055480)	Primary analysis: sensitivity analysis	Efficacy	Same as for the main analysis. Include only the data collected in the lead-in study (C0371004) and the data postinfusion of PF-07055480 in the 'Efficacy' population.	Same as above but no hypothesis testing.

Endpoint	Analysis Type	Population	Data Inclusion and Rules for Handling Intercurrent Events and Missing Data	Analysis
compared to the data collected in the lead-in study.				
Total ABR postinfusion (from Week 12 through data cutoff postinfusion of PF-07055480) with imputation	US-specific analysis	Dosed	Same as for the main analysis and the imputation rules described in Table 10 will be applied.	Same as for the main analysis with hypothesis testing.

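### The first- and latest-6-month preinfusion analyses in SAP 6.1.1.2 cannot confirm that there is no seasonal effect

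*SAP*

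**What the plan says.** SAP 6.1.1.2 plans two sensitivity analyses of Total ABR in the Efficacy population. They use preinfusion bleeding data "during only the latest 6 months and the first 6 months separately during the lead-in study up to preinfusion of PF-07055480". Two purposes are given: to support the robustness of the primary result, and to "confirm the absence of seasonal effect". The section adds that "all the participants will have the same length (i.e., 6 months) of preinfusion observation period". Like the other sensitivity analyses listed there, they are run "without hypothesis testing unless specified".

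The length of the preinfusion record is set elsewhere:

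- SAP Section 4 defines the Efficacy population as dosed participants "who have completed at least 6 months of follow up in the lead-in study", with a further condition on postinfusion follow-up.
- SAP Section 2.3 says of the participants who trigger the primary analysis: "These 50 participants will have completed at least 6 months of routine prophylaxis follow up in Study C0371004". No maximum is stated.
- The same section says: "This study will include an approximately 6-week screening (screening can be extended beyond 6 weeks when needed) and baseline period".

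The main model (SAP 6.1.1.1) contains time and time-by-treatment and no further covariates, so it has no season or calendar term. SAP Appendix 2 lists the two analyses again ("To include the bleeding data collected during only the latest 6 months and the first 6 months separately during the lead-in study") but does not repeat the seasonal purpose.

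**The concern.** A first-versus-latest split can speak to season only if the two windows cover different data and different parts of the year. Neither is required. A participant with the minimum lead-in contributes mostly the same days to both runs. Where the windows do separate, they are still early and late in that participant's follow-up, which may or may not fall in different seasons. No direct comparison of the two windows is planned; each is only compared with the postinfusion period.

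The design is single-arm and before-after with no concurrent control, so the calendar months covered before and after infusion are not balanced by design. It is therefore reasonable for the SAP to address season. Followed as written, though, the report could say that season had been ruled out when these analyses could not have detected it.

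**Working it through.** The plan gives no figure to reproduce here. The check is interval arithmetic, followed by a simple seasonal illustration.

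**Inputs**

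- Window length W = 6 months = 6 × 30.4375 = 182.6 days (SAP 6.1.1.2).
- Lead-in of at least 6 months (SAP Sections 2.3 and 4).
- Screening and baseline of about 6 weeks = 42 days, extendable (SAP 2.3).

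**Step 1: overlap.** For total preinfusion time T, shared days = max(0, 2W − T) and shared fraction = shared days / W.

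At the minimum, T = 182.6 + 42 = 224.6 days (7.4 months). Shared days = 365.25 − 224.6 = 140.6, and 140.6 / 182.6 = 77%. Only 42 days at each end differ. If screening adds no time, T = W and the windows are identical.

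| Lead-in (months) | Shared, with 42 days added | Shared, no time added |
|---|---|---|
| 6 | 77% | 100% |
| 7 | 60% | 83% |
| 8 | 44% | 67% |
| 9 | 27% | 50% |
| 10 | 10% | 33% |
| 12 | 0% | 0% |

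The windows separate fully only when T reaches 12 months, which is a lead-in of about 10.6 months plus 6 weeks. At the Protocol 9.2 planning value of 5 bleeds/year on prophylaxis, a minimum-length participant has 5 × 42 / 365.25 = 0.57 expected bleeds in the non-shared part of a window, out of 2.50 in the whole window.

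**Step 2: sensitivity to a yearly pattern.** Assume a bleed rate m(1 + A sin(2πt/Y + θ)) with Y = 365.25 days, where θ is set by the participant's entry date. Since W = Y/2, the mean rate over a window starting at s is m + (2/π)mA cos(2πs/Y + θ). The latest window starts at s = T − W, so

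latest minus first = (2/π)mA [cos(2π(T − W)/Y + θ) − cos θ],

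and its largest size over θ is (4/π)mA |sin(π(T − W)/Y)|.

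| T (months) | Largest difference, in units of mA |
|---|---|
| 6 | 0 |
| 7.4 | 0.45 |
| 9 | 0.90 |
| 12 | 1.27 |
| 18 | 0 |

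At the minimum lead-in the split can show at most 0.45 / 1.27 = 35% of the contrast available at 12 months. At 18 months the windows are disjoint but cover the same calendar months (months 0–6 and 12–18), so the contrast disappears again.

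**Step 3: average over participants.** If θ is uniform, meaning entry dates are spread evenly over the year, both cosine terms average to zero. The expected difference is then 0 for every T and every A, so agreement between the two runs is expected with or without seasonality. By the same calculation the average preinfusion rate is m, so the expected seasonal bias in the mean preinfusion rate is also 0.

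**The case against.** The strongest reply has four parts.

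1. **The 77% is an extreme.** It applies only at the minimum lead-in. The documents set no maximum, and a fixed common length of 6 months makes sense only if preinfusion lengths vary. At about 12 months the windows are disjoint and fall in opposite half-years. This stands: the overlap across the Efficacy population cannot be computed from the documents. It does not rescue the claim, because separation alone does not give a seasonal contrast (the 18-month case) and averaging over entry dates can remove it at any length.

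2. **Staggered entry works in the trial's favour.** A reader might infer that a seasonal imbalance feeds directly into the primary difference. The documents do not support that. The spread of entry dates that makes the split uninformative would also average season out of the preinfusion mean. The actual spread is not given, so a residual imbalance is possible but not shown. The documents give no size for seasonal bleeding either. The planning values (2 after infusion against 5 before, a difference of −3) lie 6 bleeds/year from the margin of +3.

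3. **Postinfusion data are not a full year for everyone.** Day 78 to Day 455 is 378 days and covers every calendar month, but the Efficacy population includes participants who discontinued earlier, and data after prophylaxis resumption are excluded. This stands, and any season-matched analysis needs a rule for them.

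4. **The phrase only states a purpose.** It belongs to sensitivity analyses without testing, and those analyses also serve robustness. This stands as to weight. It is a reason to keep both runs and correct the wording.

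**Conclusion.** The stated inference is not valid. Agreement between the two runs cannot confirm that there is no seasonal effect: the windows follow study time rather than the calendar, they share 77% to 100% of their days at the minimum lead-in, and they are disjoint only from 12 months of preinfusion data. The overlap figures rest only on the window length, the lead-in minimum and the nominal 6-week screening and baseline period. That the runs are expected to agree regardless of season rests on two assumptions of this check, a sinusoidal yearly pattern and evenly spread entry dates.

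Two stronger readings should not be drawn. The two runs cannot be called redundant for the whole population, because the distribution of lead-in lengths is not given. Nor is the primary result shown to be seasonally biased. The point is minor: it limits what the report may say about season and leaves the primary test, margin, alpha and testing sequence unchanged.

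**What to change.** 1. Keep both 6-month analyses in SAP 6.1.1.2 as robustness checks with a common preinfusion length. Replacing either would lose half of that check.
2. Delete the second purpose, "confirm the absence of seasonal effect", from SAP 6.1.1.2. Appendix 2 has no seasonal wording to remove.
3. Add one sensitivity analysis on the Efficacy population, in SAP 6.1.1.2 and Appendix 2. Restrict each participant's postinfusion data to the calendar months covered by his preinfusion window, recompute the observation time to match, and refit the main model. The eDiary already records bleed dates.
4. State a rule for participants whose postinfusion data, because of discontinuation or prophylaxis resumption, do not cover those months. For example, restrict both periods to the calendar months they share and exclude participants with none, reporting how many are excluded.

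The cost is one further run of the existing model on a date-filtered dataset. That run has less data and a wider confidence interval; no other analysis changes. Its result should be reported as the treatment difference with calendar months matched, not as proof that bleeding is not seasonal.
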